Three longitudinal biomarker substudies will evaluate the effects of study treatment on the underlying pathophysiology of AD using amyloid PET, tau PET and/or CSF biomarkers. Participation in the substudies is optional and will require specific consent that will not affect enrollment or treatment in the main study. The tau PET substudy will be offered to study-eligible subjects from select geographical sites (based on the proximity to the tau PET ligand manufacturing sites) in the United States (US) who have an amyloid positive study-specific PET scan and who have also consented to participate in the amyloid PET substudy. Tau PET scanning will be performed using a sponsor-supplied tau PET imaging agent, eg, PI-2620. . (revised per Amendments 04 and 05)

The end of the Core Study will be the date of the last study visit (Visit 15) for the last subject in the double-blind Randomization Phase. . The end of the Extension Phase will be the date of the last study visit for the last subject enrolled in the Extension Phase. (revised per Amendments 02 and 05).

Core Study

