The *ApoE* genotype for all subjects and NAT2 genotype in a subset of subjects will be determined from blood specimens using validated assays. (revised per Amendment 03)

Plasma concentrations of elenbecestat that may extend to the key metabolites M1, M2, and M5 will be measured by a validated assay using liquid chromatography method using tandem mass spectrometry.

A β (1-x) and other relevant biomarkers will be measured in the blood samples collected at times that match the PK draws and during the Follow-up Period. (revised per Amendment 01)

Statistical Methods

All statistical analyses will be performed by the sponsor or designee after the study is completed and the database is locked and released for unblinding. All statistical analyses will be performed based on the pooled data from 2 studies (E2609-G000-301 and E2609-G000-302). The analyses will also be performed within each study to confirm the trend of the efficacy and biomarker endpoints unless specified. (revised per Amendment 05)

Core Study

Study Endpoints

Primary Endpoint

- Change from baseline in the CDR-SB at 24 months in the combined studies (revised per Amendment 05)

Key Secondary Endpoints (revised per Amendment 05)

- Change from baseline in ADCOMS at 24 months in the combined studies
- Change from baseline in amyloid PET SUVR at 24 months for brain amyloid levels in the combined studies
- Change from baseline in amyloid PET SUVR at 24 months for brain amyloid levels in the individual studies

Other Secondary Endpoints (revised per Amendment 05)

- Change from baseline in the CDR-SB at 24 months for subjects enriched by baseline PET SUVR, eg, between 1.2 and 1.6, in the combined studies
- Change from baseline in the ADCOMS at 24 months for subjects enriched by baseline PET SUVR, eg, between 1.2 and 1.6, in the combined studies
- The rate of change over time (mean slope) based on CDR-SB score over 24 months in the combined studies
- Time to worsening of CDR scores by 24 months (eg, the worsening of global CDR score is defined as an increase from baseline by at least 0.5 points on the global CDR scale on 2 consecutive scheduled visits at which global CDR is undertaken) in the combined studies
- Time to conversion to dementia by 24 months for subjects who were not clinically staged as dementia at Baseline based on clinical diagnosis in the combined studies

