The rate of change over time (mean slope) based on change from baseline in the CDR-SB will be analyzed using linear mixed effects (LME) models for multivariate normal data derived from a random coefficient model (slope analysis), where the mean slope in each group depends on a continuous assessment time. The LME model will include treatment group, baseline CDR-SB, randomization stratification variables, assessment time, baseline CDR-SB-by-assessment time, and treatment group-by-assessment time. *ApoE4* status may be included in the model if appropriate.

Time to worsening of CDR scores by 24 months will be analyzed on the FAS using Cox regression model for treatment effect adjusting for randomization stratification factors. *ApoE4* status may be included in the model if appropriate. (revised per Amendment 05) Time to worsening of a CDR score

is defined as time from randomization to worsening of the CDR score (ie, the first worsening in 2 consecutive scheduled visits). For subjects whose CDR scores have not worsened by the end of the Treatment Period of the Core Study, the time to worsening of the CDR score will be censored at the date of last CDR assessment for these subjects.

Time to conversion to dementia for subjects who were not clinically staged as dementia at Baseline based on clinical diagnosis will be analyzed on the FAS using Cox regression model for treatment effect adjusting for randomization stratification factors. *ApoE4* status may be included in the model if appropriate. (revised per Amendment 05) Proportion of subjects with dementia diagnosis at 24 months will be estimated using Kaplan–Meier method based on time to conversion to dementia based on clinical diagnosis. Time to conversion to dementia for subjects who were not clinically staged as having dementia at Baseline based on clinical diagnosis is defined as time from randomization to conversion to dementia based on clinical diagnosis. For subjects without clinical dementia by the end of study, the time to conversion to dementia based on clinical diagnosis will be censored at the date of last dementia diagnosis.

The other continuous secondary efficacy endpoints as defined above will be analyzed using the same MMRM model as the primary efficacy analysis to compare elenbecestat 50 mg per day versus placebo on the FAS, using baseline value corresponding to the response variable in the model.

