Time to change of concomitant AD treatment will be analyzed similarly to that for time to conversion to dementia based on clinical diagnosis. Time to change of concomitant AD treatment is defined as time from randomization to the first dose increase and/or initiation of treatment with AChEI or memantine after randomization. For subjects without any change of concomitant AD treatment by the end of study, the time to change of concomitant AD treatment will be censored at the date of last assessment of concomitant medication.

The proportion of subjects with any change of concomitant AD treatment at 24 months will be analyzed similarly to that for proportion of subjects with dementia diagnosis at 24 months.

The rate of change over time (mean slope) based on change from baseline in the NPI-10 item will be analyzed in a manner similar to that used for the rate of change over time (mean slope) based on change from baseline in the CDR-SB.

The analysis of the following exploratory efficacy endpoints will be performed to compare elenbecestat versus placebo using the appropriate prespecified statistical methods including MMRM model, analysis of covariance model (ANCOVA), etc. For each exploratory efficacy endpoint, the treatment effect for elenbecestat 50 mg per day versus placebo will be tested at a significance level of 2-sided $\alpha = 0.05$.

- Change from baseline in NPI-10 item at 24 months
- Change from baseline in EQ-5D (subject self-reported, study partner self-reported, and subject measured by proxy) and QOL-AD (subject and study partner) at 24 months
- Change from baseline in Zarit's Burden Interview at 24 months

Additional analyses may be performed as needed.

Pharmacokinetic, Pharmacodynamic, Pharmacogenomic, and Other Biomarker Analyses

Pharmacokinetics

Safety Analysis sets will be used for individual elenbecestat plasma and CSF concentration listings. The PK Analysis Set will be used for the summaries of elenbecestat plasma and CSF concentrations.

A population PK approach will be used to characterize the PK of elenbecestat. The effect of covariates (ie, demographics) on elenbecestat PK will be evaluated. The PK model will be parameterized for clearance (CL) and volumes of distribution. Derived exposure parameters such as area under the concentration \times time curve (AUC) will be calculated from the model using the individual posterior estimate of CL and dosing history.

Pharmacokinetic-Pharmacodynamic

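### Time to conversion to dementia is defined over 24 months, but its Cox analysis runs to the end of study, which for the Core Study is Visit 15 at month 27, off drug

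*Protocol*

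**What the plan says.** All of this is in the Version 7.0 synopsis (section 2).

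- Other Secondary Endpoints sets the window: "Time to conversion to dementia by 24 months for subjects who were not clinically staged as dementia at Baseline".
- Analyses for Other Secondary Endpoints defines the event time as running from randomization to conversion, with no upper limit, and then gives the censoring rule: "For subjects without clinical dementia by the end of study, the time to conversion to dementia based on clinical diagnosis will be censored" at the last dementia diagnosis.
- The paragraph just above, on time to CDR worsening (also a 24-month endpoint), uses another limit: "For subjects whose CDR scores have not worsened by the end of the Treatment Period of the Core Study".
- Study Design states: "The end of the Core Study will be the date of the last study visit (Visit 15) for the last subject". The secondary endpoint list describes month 27 as 24 months of treatment plus 3 months of posttreatment follow-up.
- Among the exploratory endpoints, time to change of concomitant AD treatment is limited to 24 months, but its analysis begins: "For subjects without any change of concomitant AD treatment by the end of study".

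**The concern.** The endpoint list and the analysis paragraph set different windows for the same variable. A programmer who follows the analysis paragraph would count a first conversion recorded at Visit 15 as an event. One who follows the endpoint definition would censor that subject by month 24. The Cox hazard ratio differs between the two, and nothing in the synopsis says which rule governs.

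The final 12 weeks are off drug for anyone who completed treatment. The hazard ratio under the written rule therefore mixes an on-treatment comparison with a short withdrawal comparison. If the effect fades on stopping, the estimate moves towards 1. If it persists, the estimate is unbiased and slightly more precise, but it still does not describe the stated endpoint. Leaving the choice open until after unblinding would make it post hoc.

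**Working it through.** **1. Is there a plan figure to reproduce?** Not for this endpoint: the synopsis gives no event count, hazard or hazard ratio for dementia. Its only power figure is for CDR-SB. With a difference of 0.25 × 1.46 = 0.365, SD 2.05, two-sided alpha 0.05 and 90% power, n = 2 × (1.960 + 1.282)² × 2.05² / 0.365² = 663 per arm. Then 663 / 0.70 gives 948 per arm, 1896 in all, against the stated 1900. That figure reproduces and does not bear on this point.

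**2. How far apart are the cut-offs?** The Table 3 schedules of the two earlier protocol texts put Visit 13 at day 729 (week 104) and Visit 15 at day 813 (week 116). The gap is 84 days, or 12 weeks, which is 12 / 116 = 10.3% of the longer window.

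**3. Can an event be recorded there?** Both earlier Table 3 schedules mark disease staging at Visit 15. The Version 7.0 schedule (Table 5) is not in the text available. The Version 7.0 synopsis does make Visit 15 the Extension baseline, so staging there is likely but not shown.

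**4. How did the mismatch arise?** In section 9.7.1.6.2 of both earlier texts, the CDR-worsening and dementia paragraphs both ended at the end of study. In Version 7.0 the CDR paragraph was changed to the end of the Core treatment period and the dementia endpoint gained its 24-month limit. The dementia censoring sentence was not changed to match.

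**5. What could it do to the hazard ratio?** The assumptions are mine: constant hazard λ, placebo conversion p by week 104, on-drug hazard ratio 0.75, equal arms and no dropout. The tail lasts 12/52 = 0.231 years.

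Worked case, p = 30%, effect gone on stopping:
- λ = −ln(0.70) / 2 = 0.178 per year.
- Placebo: 0.300 by week 104; tail 0.700 × (1 − e^(−0.178 × 0.231)) = 0.028.
- Active: 1 − e^(−0.75 × 0.178 × 2) = 0.235 by week 104; tail 0.765 × (1 − e^(−0.178 × 0.231)) = 0.031.
- Late share = (0.028 + 0.031) / (0.300 + 0.235 + 0.028 + 0.031) = 10.0%.
- Blended hazard ratio = exp((1 − 0.100) × ln 0.75) = 0.772.

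Power uses Schoenfeld's formula, Φ(½ √d × |ln HR| − 1.96). For illustration take d = 375 events by month 24. At HR 0.75 the argument is ½ × 19.36 × 0.2877 − 1.96 = 0.825, which gives 79.5%. Events to month 27 are 375 / (1 − late share).

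| Placebo conversion by 24 months | Late share | HR | Events to month 27 | Power |
|---|---|---|---|---|
| 20% | 10.6% | 0.773 | 419 | 75.0% |
| 30% | 10.0% | 0.772 | 416 | 75.3% |
| 40% | 9.3% | 0.770 | 413 | 75.6% |
| 50% | 8.5% | 0.769 | 410 | 75.9% |

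**6. If the effect persists.** With full persistence the hazard ratio stays at 0.75, and 412 events give Φ(½ × 20.30 × 0.2877 − 1.96) = 83%. With an off-drug hazard ratio of 0.875, the lost effect and the added events nearly cancel, and power stays within 0.2 points of 79.5%.

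**7. With dropout.** A constant dropout hazard reaching the protocol's 30% by month 24 lowers the late share to about 7-9% and, with no off-drug effect, gives a hazard ratio of 0.765-0.769.

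**The case against.** The best defence is that the intended window is plain. The endpoint says 24 months, the Kaplan-Meier proportion is quoted at 24 months and is untouched by later events, and the censoring sentence is carried over from earlier text. The SAP may settle the data cut. For Version 7.0 only the synopsis is available, so the body section on secondary analyses cannot be checked. All of that lowers the stakes. It does not remove the fault: the protocol states two incompatible limits, and an SAP would have to depart from one of them.

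A reader might go further and infer that the unqualified end of study reaches into the open-label Extension, so that placebo subjects who cross over to elenbecestat enter the Cox model. Study Design does define a second end: "The end of the Extension Phase will be the date of the last study visit for the last subject enrolled". The documents do not support that inference. The dementia analysis sits under the Core Study heading, and the Extension has its own heading, its own dementia endpoint and its own methods (descriptive summaries and a delayed-start analysis). The point is confined to months 24 to 27.

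Nor does the plan wrongly count every off-drug conversion. Conversions before month 24 in subjects who stopped early count under either cut-off, in keeping with the intent-to-treat approach stated for the primary analysis.

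For change of AD treatment the mismatch is a little less certain. Section 9.7.1.5 of the earlier texts defines concomitant medication as started no later than the last dose, although it also says that follow-up medication is recorded.

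**Conclusion.** The inconsistency is real and should be corrected. As written, first conversions recorded between months 24 and 27 enter the hazard ratio of a 24-month endpoint, while the sibling endpoint excludes that period.

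The effect is modest and can go either way on power: from about 4 points lost if the effect stops with the drug to about 4 points gained if it persists fully. The hazard ratio moves from 0.75 to at most about 0.77. These sizes rest on assumed hazards, an assumed hazard ratio, an assumed event count and staging at Visit 15.

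This is an other secondary endpoint outside the key secondary hierarchy, and the AD-treatment endpoint is exploratory. Type I error control, the sample size and the primary analysis are not affected. Under these assumptions any dilution is towards the null, so it would not create a false positive.

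**What to change.** In the dementia paragraph and the AD-treatment paragraph, replace the end-of-study limit with the one already used for CDR worsening ("have not worsened by the end of the Treatment Period of the Core Study"). Censor at the last staging assessment, or the last concomitant-medication assessment, on or before that time. State that the limit is month 24 (Visit 13) counted from randomization, not each subject's own last dose, so that off-drug conversions before month 24 in early discontinuers still count. Report conversions after month 24 descriptively. If 27 months was intended, change the two endpoint definitions instead. Make the same edit in the body text if it repeats the phrase, and settle it before unblinding.

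The cost is one phrase in two paragraphs and, under the assumptions above, roughly 7-11% fewer events in the dementia model.

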Subjects who discontinue study drug early must complete the ED Visit (within 7 days of the last dose of study drug) and the Follow-up Visits (1 and 3 months after the last dose of study drug). These Follow-up Visits will be conducted to monitor efficacy and safety parameters after early withdrawal from the study or discontinuation of study drug.

All subjects in the Core Study who discontinue study drug before reaching 12 months of treatment during the Core Study will also be asked to return to the clinic for a 12-month clinical assessment and then again at 24 months. Subjects who discontinue treatment between 12 and 24 months of treatment will be asked to return to the clinic for a 24-month clinical assessment. Subjects who discontinue early from study drug are considered “on study” as long as they continue to return for their clinical assessments at 12 and 24 months as outlined above, at which efficacy and quality of life will be assessed along with concomitant medications. New AEs will be collected for 4 weeks post last dose and followed-up for 12 weeks, or until resolution, whichever comes first. AEs relating to study procedures will be collected until the end of study participation. (revised per Amendment 05) However, subjects who discontinue study drug early are not considered to have ‘completed’ the study as a final Subject Disposition.

Data Safety Monitoring Board

An independent Data Safety Monitoring Board (DSMB) will convene at regular intervals to monitor the overall safety of the study and to make recommendations to the sponsor related to study safety as appropriate. The DSMB will be asked to review the cumulative safety data, which includes measures of cognitive safety at the group level, up to the date identified to make a determination if the trial is safe to proceed unchanged or to provide recommendations to the sponsor as to how to proceed. The study will proceed, including randomization of additional subjects, during DSMB safety reviews. Details will be provided in the DSMB Charter. (revised per Amendment 05)

Extension Phase

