The following biomarker endpoints will be summarized by descriptive statistics and graphs:

- Change from baseline in amyloid PET SUVR
- Change from baseline in tau PET signal
- Change from baseline in total hippocampal volume as measured by vMRI
- Change from baseline in the preservation of connectivity as measured by fMRI
- Change from baseline in t-tau, p-tau, A β (1-42) and A β (1-x) in CSF
- Change from baseline in A β (1-x) in plasma
- Change from baseline in exploratory biomarkers eg, NFL, VILIP1, YKL-40, and Ng in CSF and plasma

A delayed-start analysis and MMRM model will be used to analyze these biomarker endpoints. The relationship between efficacy endpoints and biomarker endpoints will be explored using correlation analysis.

Interim Analyses

This is a fixed design. There is no interim analysis of efficacy and no alpha spending before final analysis. However, a futility analysis is planned when approximately 30% subjects in the combined

2 studies (E2609-G000-301 and E2609-G000-302) have had an opportunity to complete the 24-month visit of the Core Study by the interim cutoff date. The sponsor may stop the trial for futility with nonbinding futility boundary calculated using conservative O'Brien-Fleming boundary of Lan-DeMets alpha spending function with 30% information based on completers. If the actual percent information of the futility analysis is different from 30%, the futility boundary will be recalculated using the actual percent information at the time of the futility analysis. A blinded sample size re-estimation through estimated standard deviation based on blinded data before the completion of enrollment, will be performed if there is an indication that sample size assumptions need to be changed. This blinded sample size re-estimation could be performed based on signals from external studies or based on review of blinded data from this study before completion of enrollment. The standard deviation of the primary endpoint was originally estimated based on data from the ADNI study. It is possible that the standard deviation for the same endpoint in clinical trials may be larger than that from this observational study. (revised per Amendment 05)

Sample Size Rationale

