The sample size for this study is estimated for comparison of elenbecestat versus placebo with respect to a pooled analysis of studies E2609-G000-301 and E2609-G000-302 for the change from baseline in CDR-SB at 24 months. Based on the available data from the placebo group in Study BAN2401-G000-201 (a recently completed study with a comparable subject population), the mean and the standard deviation of the change from baseline in CDR-SB at 24 months in the placebo group are assumed to be 1.46 and 2.05, respectively, instead of 1.75 and 2.05, which are originally assumed by the available data from ADNI (of amyloid positive, MMSE equal or greater than 24, late MCI [global CDR=0.5, CDR memory box \geq 0.5]) is selected to estimate the mean and standard deviation of the change from baseline in CDR-SB at 24 months in the placebo group, which are 1.5 and 2.05, respectively. Therefore, assuming a 25% reduction in the mean change from baseline CDR-SB at 24 months for elenbecestat compared to placebo with common standard deviation of 2.05 and 30% dropout rate, a total sample size of 1900 subjects, 950 subjects in each treatment group, will be required to detect the treatment difference between elenbecestat and placebo using a 2-sample t test with 90% power at a significance level of 2 sided alpha =0.05.

The pooled data from 2 studies (E2609-G000-301 and E2609-G000-302) will comprise the total sample size of approximately 1900 subjects. At least 850 subjects will be randomized in each study. (revised per Amendment 05)

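### The futility boundary is specified through an alpha-spending function; taken literally it gives no usable threshold, and it should name beta spending (or conditional power) and a direction

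*Protocol*

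**What the plan says.** The Version 7.0 synopsis (Interim Analyses) describes a fixed design: "There is no interim analysis of efficacy and no alpha spending before final analysis". It then plans a futility analysis once about 30% of the subjects pooled over Studies 301 and 302 have had the chance to reach the 24-month visit. The stopping rule reads: "The sponsor may stop the trial for futility with nonbinding futility boundary calculated using conservative O'Brien-Fleming". As the source of the limit it names the "boundary of Lan-DeMets alpha spending function with 30% information based on completers". It adds: "If the actual percent information of the futility analysis is different from 30%, the futility boundary will be recalculated using the actual percent information".

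The synopsis gives no beta level, direction, cut-off or conditional-power threshold for this look. The same method stands in the synopsis and Section 9.7.3 of the earlier protocol versions in the file. Amendment 05 revised the timing of the look and kept the method. The Version 7.0 body text of Section 9.7.3 is not in the file, so for the current version only the synopsis could be checked.

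The design parameters are in Sample Size Rationale in the same synopsis. The calculation is made "using a 2-sample t test with 90% power"; the test is run "at a significance level of 2 sided alpha =0.05". It assumes a 25% reduction in mean decline, 30% dropout and 1900 subjects. The placebo mean and SD of the CDR-SB change "are assumed to be 1.46 and 2.05, respectively, instead of 1.75 and 2.05".

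**The concern.** A spending function for alpha limits the chance of wrongly rejecting the null at an interim look. With an O'Brien-Fleming shape it is deliberately extreme early on, because it guards against premature claims of efficacy. A futility boundary answers a different question: how much type II error may be used up by stopping a trial that would have succeeded, or how low the chance of final success must be. It needs a beta or a conditional-power criterion.

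The protocol does not leave the method open for the SAP. It fixes one, names the wrong error type, and requires recalculation from that same function if the information differs from 30%. A statistician implementing the sentence must guess what was meant, and the guesses differ by about 3 to 5 units of Z. A decision to stop or continue could then not easily be defended as prespecified.

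**Working it through.** **Inputs (Version 7.0 synopsis).** Two-sided alpha 0.05, so 0.025 per side; power 90%, so beta = 0.10; placebo mean change 1.46; SD 2.05; effect 25% of 1.46 = 0.365; dropout 30%; 1:1 allocation; total 1900; information fraction t = 0.30. Positive Z means benefit.

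**The plan's own figure first.** n per arm = 2 x 2.05² x (1.960 + 1.282)² / 0.365² = 663 after rounding up. Dividing by 0.70 gives 948 per arm, 1896 in total (1898 with the exact t test). This reproduces the stated 1900. The same paragraph also gives a placebo mean of 1.5, which would give 1798; the 1.46 figure is therefore used here.

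**Expected Z at the look.** Drift at full information = 1.960 + 1.282 = 3.242. At t = 0.30 the expected Z under the planned effect is 3.242 x √0.30 = 1.775, and 0 under no effect.

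**The function as named.** O'Brien-Fleming-type Lan-DeMets spending is 2 x [1 - Φ(z(1 - a/2)/√t)]. With a = 0.025 and t = 0.30 this is 0.0000427, so |Z| = 3.93.

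- *Stop if Z < -3.93.* Under no effect: 0.004%. Under the planned effect: about 6 in 10⁹. Assuming 1900 x 0.30 x 0.70 = 399 subjects with 24-month data, the SE is 2.05 x √(2/199.5) = 0.205, so the drug would have to look 3.93 x 0.205 = 0.81 CDR-SB points worse than placebo.
- *Stop unless Z > 3.93.* Under the planned effect: Φ(3.93 - 1.775) = 98.4%. Under no effect: 99.996%. If obeyed, power would be about 1.6%.

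The alpha convention does not rescue either reading. Spending 0.05 two-sided gives |Z| = 3.58, with 96.4% stopped under the planned effect on the second reading and about 0.02% under no effect on the first. Spending 0.05 one-sided gives 3.39, with 94.7% and 0.03%.

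**The same shape applied to beta.** With a = 0.10 and t = 0.30, the beta spent is 0.0027, whose normal quantile is -2.786. The cut-off is 1.775 - 2.786 = -1.01.

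| Rule at t = 0.30 | Stops, no effect | Stops, planned effect |
|---|---|---|
| Z < -3.93 | 0.004% | about 6 in 10⁹ |
| unless Z > 3.93 | 99.996% | 98.4% |
| Z <= -1.01 (beta = 0.10) | 15.6% | 0.27% |

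With the beta rule, overall power is 89.9% against 90.0% with no look, and the one-sided type I error is 0.0249 if the rule is followed.

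**Does recalculation at the actual fraction help?** No. At t = 0.40 (665 evaluable per arm, drift 3.247) the alpha function gives |Z| = 3.36. Stopping below -3.36 occurs in 0.04% of null trials, and stopping unless Z > 3.36 in 90.4% of trials with the planned effect. The beta version gives Z <= -0.30, stopping 38% and 0.93%.

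**The case against.** The strongest reply is that alpha is a slip of the pen. Lan-DeMets O'Brien-Fleming is often used loosely for the shape of the curve, and applied to beta it makes a sensible, cautious rule. The reading that stops unless Z > 3.93 turns a futility look into an efficacy hurdle, which sits badly in a paragraph that disclaims any efficacy interim. The boundary is also nonbinding. All this stands: the two literal readings are not the only ones, and a workable one exists. But the text neither says beta nor gives its level.

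A second reply is that an SAP or charter may hold the number. That covers the missing cut-off and stopping probabilities. It does not cover the error type, which the protocol itself states.

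Three stronger inferences are tempting, and the documents do not support them.

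- *That the paragraph contradicts itself by disclaiming alpha spending.* A nonbinding futility look spends no type I error whatever curve shapes its limit, so that sentence remains true. The clash is one of wording.
- *That this is the only route to stopping early.* Section 11.11 in the earlier versions, still listed in the Version 7.0 contents, lets the sponsor discontinue at any time for any reason. The DSMB also reviews cumulative safety data, including cognitive safety, and may recommend how to proceed.
- *That basing information on completers conflicts with an analysis that keeps data after drug discontinuation.* The synopsis does say: "However, subjects who discontinue study drug early are not considered to have" completed, but it says so of final subject disposition. In the futility paragraph the word follows a trigger about reaching the 24-month visit and can naturally mean subjects with 24-month data.

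**Conclusion.** The point holds in limited form. The protocol attaches the wrong error type to its futility boundary. Taken literally, the threshold is |Z| = 3.93 at 30% information, which either practically never stops an ineffective drug's trial or flags 98.4% of trials with the planned effect. Against the beta-spending cut-off of -1.01, the literal cut-offs lie 3.93 - 1.01 = 2.92 and 3.93 + 1.01 = 4.94 units of Z away.

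The consequence is bounded. Type I error is untouched and no stop is compelled. If the lower literal limit were used, power would be unaffected and the loss would be the 15.6% chance of ending a futile programme at this look. This is a should-fix.

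The figures assume the stated 90% power at the planned effect, 30% information at the look, and beta = 0.10. The last is inferred from the power; the protocol does not state it for futility.

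**What to change.** In Interim Analyses (and in Section 9.7.3 if it reads the same), replace the alpha-spending function by an O'Brien-Fleming-type Lan-DeMets beta-spending function with its level. Beta = 0.10 matches the stated power. State the direction: stopping may be considered when Z, signed so that benefit is positive, falls at or below the boundary, about -1.01 at 30% information. A conditional-power rule with a prespecified threshold and assumed effect would serve equally well. The stopping probabilities under no effect and under the planned effect can go in the SAP.

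At most, add a clause saying that completers means subjects with 24-month CDR-SB data.

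The cost is one or two sentences. Sample size, timing and the final test do not change, power falls from 90.0% to about 89.9% if the rule is followed, and type I error does not rise.
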